6. ANALYSES AND SUMMARIES

Both the FAS and PPAS populations will be used in the analyses of the primary efficacy endpoint, with the FAS being primary. For all other efficacy endpoints, only the FAS analysis set will be utilized.

For all efficacy analyses and summaries (Sections 6.1, 6.2, 6.3 {except CCI [REDACTED]} and 6.4): All data collected for subjects consented under Protocol Amendment 2 prior to entering Period B will be included for modelling and summaries. Otherwise, only data collected through Week 10 (Period A) will be included for subjects who do not meet the above condition, and their data collected after Week 10 will be in listings only.

6.1. Primary Endpoint(s)

6.1.1. Change from Baseline in Daily OFF time at Week 10 (end of Period A)

6.1.1.1. Primary Analysis

Endpoint: Daily OFF time

- Analysis time points: Week 10 (End of Period A)
- Analysis population (method of imputation for missing data): FAS (See Section 3.1)
- Analysis methodology

Change from baseline will primarily be analyzed using the Bayesian Dose Response Analysis (See Section 5.2.2.3.2). If the Bayes posterior predictive test rejects the monotonic Emax fit (prob < 0.05), then the primary analysis will be based on the MMRM analysis (See Section 5.2.2.1). An overall dose-response trend test (See Section 5.2.2.4) will also be performed to control family-wise error rate.

- Supporting objective and Decision rule: Primary Objective (See [Section 2.1.1](#)), Secondary Objective (See [Section 2.1.2](#)), and Decision rules C1, C2 (See [Section 5.1.2](#))

Reporting results:

- Raw data: The sample size, mean, standard deviation, median, minimum and maximum at baseline and post-baseline visits will be presented for each treatment arm.
- Change from baseline: The sample size, mean, standard deviation, median, minimum and maximum will be presented for each treatment arm. The Bayesian point estimates, 90% credible interval, difference from placebo for each pair of treatment groups and the corresponding 90% credible interval will be presented. The MED estimate if applicable will be presented.

Figures

- Vertical bar chart of Change from Baseline Bayesian point estimates and 90% credible interval at Week 10.
- Bayesian Emax model graph with the MMRM estimates.
- Change from baseline time profile per MMRM for each treatment group.

6.1.1.2. Sensitivity/Robustness Analyses

To support the interpretation of the primary analysis the following analyses will be performed:

Endpoint: Daily OFF time

- Analysis time points: Week 10 (End of Period A);
- Analysis populations (method of imputation for missing data): FAS, PPAS, FAS-Cohort 1 only, FAS-Cohort 2 only (See [Section 3.1](#));
- Analysis methodology: Change from baseline will be analyzed using the MMRM analysis (See [Section 5.2.2.1](#); FAS, FAS-Cohort 1 only), Bayesian ANOVA analysis (See [Section 5.2.2.3.1](#); FAS, FAS-Cohort 1 only), Dose Response analysis (See [Section 5.2.2.2](#); FAS, FAS-Cohort 2 only), and Bayesian Dose Response analysis (See [Section 5.2.2.3.2](#); PPAS, FAS-Cohort 2 only).

Reporting results:

- Raw data: The missing data pattern will be shown by treatment group and overall, for the Hauser Diary up to Week 10.
- Change from baseline: The point estimate, 90% confidence or credible interval for the point estimate, difference from placebo for each pair of treatment groups and the corresponding 90% confidence or credible interval will be presented. The MED estimate if applicable will be presented.

Figures

- Empirical cumulative distribution function showing % of subjects with change from baseline \leq cutoff value at Week 10 by treatment group; (any drop outs are assigned to the left side of x axis).

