## **7.3. Efficacy Measures**

### **7.3.1. OFF Time Diary (Hauser Diary)**

In patient diaries, “OFF” time is defined as a period when medication has worn off and is no longer providing benefit with regard to mobility, slowness, and stiffness. During this period, Parkinson’s disease patients experience relatively poor overall function with worsening of tremor, rigidity, balance, or bradykinesia. “ON” time is defined as the time when medication is providing benefit with regard to mobility, slowness, and stiffness. “ON” time can be classified as associated with or without troublesome dyskinesia that interfere with activities of daily living. It has been demonstrated that “OFF” time and “ON” time with troublesome dyskinesia are generally considered by patients to be “bad time” with regard to motor function, whereas “ON” time without dyskinesia and on time with non-troublesome dyskinesia are generally considered to be “good time”.

Currently, available diaries are designed to record patient motor state for half hour intervals. These diaries are a way for patients to assess their own health status without clinician bias or interpretation. Diaries are especially useful in understanding symptoms’ temporal dynamics, including triggers that exacerbate symptoms. They also help individuals to evaluate the impact of their treatment.

For the purposes of this study, a paper Hauser diary will be utilized. Entries are made on the days noted in the [STUDY PROCEDURES](#) section of the protocol. Training on the diary will be provided to sites and subjects. Subjects will complete the diary for three consecutive days in the week prior to each visit (except Day 28 visit) as indicated in the [STUDY PROCEDURES](#) section, including three consecutive days during the week prior to Day 0 (Randomization).

CCI

CCI

CCI

CCI

CCI

A large black rectangular redaction box covering the majority of the page content.

CCI

A large black rectangular redaction box covering the majority of the page content.

[figure not shown]
CCI

A large black rectangular redaction box covering the majority of the page content.

CCI

A large black rectangular redaction box covering the majority of the page content.

CCI

[figure not shown]
CCI

CCI

CCI

CCI

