3.2. Secondary Endpoint(s)

Secondary endpoints evaluated during the entire double-blind period include:

- Daily OFF time (hours): change from baseline in average daily OFF time by Visit.
- Daily ON time with troublesome dyskinesia (hours): change from baseline in average daily ON time with troublesome dyskinesia by Visit.
- Daily ON time without troublesome dyskinesia (hours): the change from baseline in average daily ON time without troublesome dyskinesia (i.e. without dyskinesia or with non-troublesome dyskinesia, or alternatively “good time”) by Visit.

The same algorithm and rules employed for the calculation of OFF time will be used for the secondary variables. Baseline is defined using the 3 Hauser diary days prior to Day 0.

- MDS – Unified Parkinson’s Disease Rating Scale (MDS-UPDRS) Part III: Change from Baseline in MDS-UPDRS Part III Score by Visit.
- MDS-UPDRS Parts I, II, IV, and total score: Change from Baseline in the MDS-UPDRS Parts I, II, IV and Total Scores by visit.

The MDS-UPDRS will be collected at times specified in the STUDY PROCEDURES section of this protocol. *Although not required, every effort should be made to have the same individual perform the ratings for an individual subject throughout the course of the study.*

MDS-UPDRS Part III should be assessed consistently and approximately 2 to 4 hours following L-Dopa dose (except at screening).

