3.2.1. MDS-UPDRS Part III

MDS-UPDRS Part III assesses the motor signs of Parkinson's disease and is administered by the investigator. It is comprised of 33 sub-scores based on 18 items, several with right, left or other body distribution scores. Each question is anchored with five responses that are linked to commonly accepted clinical terms: 0 = normal, 1 = slight, 2 = mild, 3 = moderate, and 4 = severe. Assessments will be done at times specified in the STUDY PROCEDURES section of the protocol. Higher total scores indicate more severe motor signs of Parkinson's disease. There are four subscales:

- The tremor subscale, which is the sum of scores for resting tremor amplitude in five body parts (5 items: right upper extremities, left upper extremities, right lower extremities, left lower extremities, and lip/jaw), postural tremor (2 items) and Kinetic tremor (2 items) in the hands (range 0–36).

If more than 1 item (>20%) is missing for a time point, the subscale score for that time point is missing; otherwise, the subscale score will be imputed as follows: sum of the non-missing items X (total number of items)/ (number of items non-missing).

- The rigidity subscale is the sum of rigidity scores for limbs and neck (5 items, range 0–20).

The subscale score will be missing if more than 1 item (>20%) is missing.

- The bradykinesia subscale is the sum of scores for finger tapping (2 items), hand movements (2 items), pronation and supination movements (2 items), toe tapping (2 items) and Global spontaneity of movement (body bradykinesia) (1 item) (range 0–36).

If more than 1 item (>20%) is missing for a time point, the subscale score for that time point is missing; otherwise, the subscale score will be imputed as follows: sum of the non-missing items X (total number of items)/ (number of items non-missing).

- The PIGD subscale is the sum of gait (1 item), freezing of gait (1 item) and postural stability (1 item) (range 0-12).

The subscale score will be missing if more than 1 item (>20%) is missing.

If more than 7 of the MDS-UPDRS Part III items are missing for a time point,⁵ the part score for that time point is missing; otherwise, the part score will be imputed as follows: sum of the non-missing items X (total number of items)/ (number of items non-missing).

Baseline will be the Day 0 measurement.

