3.2.2. MDS-UPDRS Parts I, II, IV, and Total Score

MDS-UPDRS Parts I, II, and IV will be done at times specified in the STUDY PROCEDURES section of the protocol. Each question is anchored with five responses that are linked to commonly accepted clinical terms: 0 = normal, 1 = slight, 2 = mild, 3 = moderate, and 4 = severe. Higher part and total scores indicate more severe signs of Parkinson's disease.

- Part I: Non-Motor Aspects of Experiences of daily Living (nM-EDL); this portion of the scale assesses the non-motor impact of Parkinson's disease on patients' experiences of daily living. There are 13 questions. Part 1A is administered by the rater (six questions) and focuses on complex behaviors. Part 1B is a component of the self-administered Patient Questionnaire that covers seven questions on non-motor experiences of daily living. (range 0-52)

If more than 1 item is missing for a time point,⁵ the part score for that time point is missing; otherwise, the part score will be imputed as follows: $\text{sum of the non-missing items} \times (\text{total number of items}) / (\text{number of items non-missing})$.

- Part II: Motor Aspects of Experiences of Daily Living (M-EDL); this portion of the scale assesses the motor impact of Parkinson's disease on patients' experiences of daily living. There are 13 questions. (range 0-52)

If more than 2 items are missing for a time point,⁵ the part score for that time point is missing; otherwise, the part score will be imputed as follows: $\text{sum of the non-missing items} \times (\text{total number of items}) / (\text{number of items non-missing})$.

- Part IV: Motor Complications; in this section, the rater uses historical and objective information to assess two motor complications, dyskinesias and motor fluctuations that include OFF-state dystonia. Use all information from patient, caregiver, and the examination to answer the six questions that summarize function over the past week including today. (range 0-24)

The part score will be missing if any underlying question is missing.⁵

[figure not shown]
- MDS-UPDRS Total Score: The sum of Parts I, II, III, and IV.

The total scores will be missing if any underlying part score is missing.

Baseline will be the Day 0 measurement.

[figure not shown]
CCI

CCI

[figure not shown]
090177e18f6e873a\Approved\Approved On: 26-Sep-2018 05:14 (GMT)

CCI

090177e18f6e873a\Approved\Approved On: 26-Sep-2018 05:14 (GMT)

CCI

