5.1.2. Statistical Decision Rules

The decision criteria for efficacy are given as below, which will be based on a Bayesian interpretation of the results:

- C1: Point estimate of PF-06649751 vs. placebo effect ≥ 1.5 hours, and
- C2: 95% confident of PF-06649751 vs. placebo effect ≥ 0 .

Better is defined as a reduction in the daily OFF time.

No adjustments for the interim analysis or multiple comparisons will be made.

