6.2. Secondary Endpoint(s)

6.2.1. Hauser Home Diary

Endpoints: Daily OFF time, Daily ON time with troublesome dyskinesia and Daily ON time without troublesome dyskinesia

- Analysis time points: All Visits;
- Analysis population (method of imputation for missing data): FAS (See [Section 3.1](#));
- Analysis methodology: Change from baseline will be analyzed using the MMRM Analysis (See [Section 5.2.2.1](#)) and Dose Response Analysis (Daily ON time without troublesome dyskinesia at Week 10 only, See [Section 5.2.2.2](#));
- Supporting objective and Decision rule: Primary Objective (See [Section 2.1.1](#)), Secondary Objective (See [Section 2.1.2](#))

Reporting results:

- Raw data: The sample size, mean, standard deviation, median, minimum and maximum at baseline and post-baseline visits will be presented for each treatment arm.
- Change from baseline: The sample size, mean, standard deviation, median, minimum and maximum will be presented for each treatment arm. The point estimate, 90% confidence interval for the point estimate, difference from the placebo for each pair of treatment groups and the corresponding 90% confidence interval will be presented.

Figures (Daily ON time with troublesome dyskinesia, without troublesome dyskinesia)

- Line graphs of LS means and 90% confidence interval at all post-baseline visits.
- Vertical bar chart of LS means and 90% confidence intervals at Week 10.
- Empirical cumulative distribution function showing % of subjects with change from baseline \leq cutoff value at Week 10 by treatment group; (any drop outs are assigned to the left side of x axis)
- Dose response Emax model graph with the MMRM estimates at Week 10.

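### One left-of-axis dropout rule serves Week 10 distribution plots with opposite benefit directions; on an ascending axis it draws dropouts as best responders for seven of eight visible endpoints, OFF time included

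*SAP*

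**What the plan says.** SAP 6.1.1.2 lists an empirical cumulative distribution figure for Week 10 change in daily OFF time, by treatment group, with the instruction that "any drop outs are assigned to the left side of x axis". The section opens with "To support the interpretation of the primary analysis the following analyses will be performed", so this figure is meant to help readers interpret the primary result.

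SAP 6.2.1 repeats the instruction under "Figures (Daily ON time with troublesome dyskinesia, without troublesome dyskinesia". SAP 6.2.2 repeats it for the MDS-UPDRS, whose endpoint line names Parts I, II, III, IV and the total. None of the three sections gives the direction of the x axis, says whether dropouts are meant as good or bad outcomes, or defines a dropout.

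The documents do fix the direction of benefit:

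- OFF time (SAP 5.1.2): "Better is defined as a reduction in the daily OFF time".
- ON time with troublesome dyskinesia (Protocol 7.3.1): OFF time and ON "time with troublesome dyskinesia are generally considered by patients to be" bad time.
- ON time without troublesome dyskinesia (SAP 3.2): defined as time "without dyskinesia or with non-troublesome dyskinesia, or alternatively" good time.
- MDS-UPDRS Part III (SAP 3.2.1): "Higher total scores indicate more severe motor signs of" Parkinson's disease.
- MDS-UPDRS Parts I, II, IV and total (SAP 3.2.2): "Higher part and total scores indicate more severe signs of" Parkinson's disease.

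**The concern.** A plot of the percentage at or below a cutoff is normally drawn with the cutoff rising from left to right. The left end is then the largest fall from baseline. A subject placed there counts as at or below every cutoff, so the whole curve is lifted by that arm's share of dropouts. Where a fall is good, a higher curve reads as benefit, and an arm that loses more subjects looks more effective.

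Unequal loss between arms is possible. The final step to 15 mg starts on Day 22, after the Week 3 diary period, so a subject with a usable Week 3 diary may leave after that step and have no Week 10 value. What is at stake is how the figures read, chiefly the OFF-time figure offered in support of the primary analysis.

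**Working it through.** **Step 1: count endpoints and directions.**

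| SAP section | Endpoints | Fall is better | Rise is better |
|---|---|---|---|
| 6.1.1.2 | OFF time | 1 | 0 |
| 6.2.1 | ON time with, and without, troublesome dyskinesia | 1 | 1 |
| 6.2.2 | MDS-UPDRS I, II, III, IV, total | 5 | 0 |
| Total | 8 | 7 | 1 |

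If all axes ascend, left is the best end for 7 of 8. If all descend, left is the best end for 1 of 8 (ON time without troublesome dyskinesia). No common direction suits all eight. The rule works throughout only if each axis runs from worse to better, which the SAP does not say.

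**Step 2: formulas for OFF time on an ascending axis.** Let d be the share with no Week 10 value, c the cutoff, and p = Φ((c − mean)/SD) among those observed.

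- Dropouts on the left: d + (1 − d)p. With no drug effect, active minus placebo = (d1 − d0)(1 − p).
- Dropouts on the right: (1 − d)p. With no drug effect, active minus placebo = −(d1 − d0)p.

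Only the difference in missing shares matters, not their level.

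**Step 3: inputs.** The SD of 2.9 h is from Protocol 9.1. The mean of −1.0 h is the placebo prior mean in SAP 5.2.2.3. The cutoff of −1.5 h is chosen for illustration. Normality and every missing share are assumptions; the 10% in Protocol 9.1 covers non-evaluable subjects and losses before Week 5, so it does not anchor them. The plan gives no figure of its own for these plots.

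**Step 4: results with no drug effect.** At −1.5 h, p = Φ(−0.5/2.9) = 0.432.

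| Missing, placebo vs active | Left placement | Difference | Right placement | Difference |
|---|---|---|---|---|
| 10% vs 10% | 48.8% vs 48.8% | 0 | 38.8% vs 38.8% | 0 |
| 10% vs 15% | 48.8% vs 51.7% | +2.8 | 38.8% vs 36.7% | −2.2 |
| 10% vs 20% | 48.8% vs 54.5% | +5.7 | 38.8% vs 34.5% | −4.3 |
| 10% vs 25% | 48.8% vs 57.4% | +8.5 | 38.8% vs 32.4% | −6.5 |

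At 10% vs 20% and other cutoffs: at −3 h (p = 0.245), +7.5 left and −2.5 right; at 0 h (p = 0.635), +3.7 left and −6.3 right.

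**Step 5: compare with sampling noise.** Arm sizes are 18 + 18 = 36 on placebo, 36 + 18 = 54 on 15 mg and 36 on each other dose. From 48.8% and 54.5%, the standard error of the difference is √(0.488·0.512/36 + 0.545·0.455/36) = 11.8 points, or 10.7 points with 54 in the second term. The 5.7-point shift is below one standard error, but it always favours the arm with more loss.

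**Step 6: who counts as a dropout.** SAP 5.3 assigns data collected at an early-termination visit to the nearest planned visit. For the diary this means Week 10 from about Day 53, since (35 + 70)/2 = 52.5. A diary value also needs valid days under rules 8 to 11 of SAP 3.1, so such a leaver may or may not have one. A subject who stays in the trial but has no valid Week 10 diary day has no value under rule 11 and is not a dropout in the ordinary sense. The instruction does not say how it treats either case.

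**The case against.** The strongest reply is that nothing decisive depends on these figures. No decision rule uses them, the shifts above are within sampling noise, and SAP 6.1.1.2 also reports the missing-diary pattern by arm. With left placement, each curve even starts at its own dropout share. All of this stands, and it limits the point to presentation.

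A reader might infer that the SAP does plot dropouts as responders in seven figures. The documents do not support that much: the axis direction is unstated, and axes set endpoint by endpoint would remove the problem. The count of eight is also a reading. The figure list in SAP 6.2.2 names no endpoints, so all five scores are taken from its endpoint line, and part of the SAP's efficacy text is redacted.

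A reader might also infer that the arms will differ in loss. That is not established. A blinded step-down is available after Day 21 (SAP 2.2), which gives some subjects an alternative to leaving. A leaver after Day 22 is not necessarily in the full analysis set: after a Week 3 phone visit the Week 3 diary is collected only at Week 4, and may never be handed in. Discontinuations in the open-label, uncontrolled Phase 1b study say little about differences between arms here.

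It can also be said that observed cases are the SAP's default (5.3 and Appendix 1), so a continuing subject without a value would simply be left out. That is a fair default reading, but the dropout instruction departs from it without saying for whom. Finally, the SAP never adopts worst-end placement, which has its own distortion and at 0 h moves the curves more than left placement does (6.3 against 3.7 points). That stands and shapes the fix.

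**Conclusion.** The point holds as an inconsistency in a stated rule. One placement cannot suit endpoints with opposite benefit directions, and on the conventional axis it flatters the arm with more dropouts in the OFF-time figure. With no drug effect the false gain at −1.5 h is 0.57 points per percentage point of difference in missing shares: 5.7 points at an assumed 10% against 20%, and none at equal shares. This rests on an ascending axis, a normal distribution and the assumed shares.

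It would be wrong to infer that the efficacy conclusion is biased. C1, C2, the Bayesian Emax and MMRM estimates, the trend test and the sample size do not use these plots. The point should be fixed because the repair is cheap and the OFF-time figure is billed as support for the primary analysis.

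**What to change.** Before the blind is broken for the final analysis, amend SAP 6.1.1.2, 6.2.1 and 6.2.2 as follows:

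1. State the axis direction.
2. Replace the left-side instruction with placement at the unfavourable end for that endpoint. On an ascending axis this is the right for OFF time, ON time with troublesome dyskinesia and all five MDS-UPDRS scores (the curve then levels off below 100%), and the left for ON time without troublesome dyskinesia.
3. Define the group as full analysis set subjects with no Week 10 value after the early-termination rule (SAP 5.3) and, for diary endpoints, the diary-validity rules (SAP 3.1, rules 8 to 11). Include subjects still in the trial.
4. Keep all full analysis set subjects in the denominator and print the number missing per arm.
5. Say that this is a conservative convention: in the 10% against 20% example it costs the arm with more missing data 4.3 points at −1.5 h. Show an observed-case curve beside it, in line with SAP 5.3; that curve shows no shift if the missing subjects resemble those observed.

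The cost is one phrase in each of three sections, one definition, one programming flag and a companion curve. No new data are needed.

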6.2. Secondary Endpoint(s)

6.2.1. Hauser Home Diary

Endpoints: Daily OFF time, Daily ON time with troublesome dyskinesia and Daily ON time without troublesome dyskinesia

- Analysis time points: All Visits;
- Analysis population (method of imputation for missing data): FAS (See [Section 3.1](#));
- Analysis methodology: Change from baseline will be analyzed using the MMRM Analysis (See [Section 5.2.2.1](#)) and Dose Response Analysis (Daily ON time without troublesome dyskinesia at Week 10 only, See [Section 5.2.2.2](#));
- Supporting objective and Decision rule: Primary Objective (See [Section 2.1.1](#)), Secondary Objective (See [Section 2.1.2](#))

Reporting results:

- Raw data: The sample size, mean, standard deviation, median, minimum and maximum at baseline and post-baseline visits will be presented for each treatment arm.
- Change from baseline: The sample size, mean, standard deviation, median, minimum and maximum will be presented for each treatment arm. The point estimate, 90% confidence interval for the point estimate, difference from the placebo for each pair of treatment groups and the corresponding 90% confidence interval will be presented.

Figures (Daily ON time with troublesome dyskinesia, without troublesome dyskinesia)

- Line graphs of LS means and 90% confidence interval at all post-baseline visits.
- Vertical bar chart of LS means and 90% confidence intervals at Week 10.
- Empirical cumulative distribution function showing % of subjects with change from baseline \leq cutoff value at Week 10 by treatment group; (any drop outs are assigned to the left side of x axis)
- Dose response Emax model graph with the MMRM estimates at Week 10.

